**(2.) Project Title and Abstract**

A Randomized Controlled Trial Comparing Brief Peer Supported webSTAIR to Waitlist

This study will enroll 350 Veterans at a 2:1 ratio where 200 Veterans will be enrolled into a brief peer supported webSTAIR (BPS webSTAIR) and 100 will be supported into Waitlist. The purpose of the study is to assess the efficacy BPS webSTAIR in regard to four outcomes: reduction in PTSD and depression symptoms (measured by the PCL-5 and PHQ-8, respectively) and improvement in emotion regulation and work and social adjustment (measured by the DERS-16 and WSAS, respectively). The active treatment is a 6-session modular treatment that focuses on learning emotion management skills where Veterans will have 10 weeks to complete the treatment. Assessments will occur three times for those in webSTAIR: baseline, post-treatment (10 weeks after randomization) and 8-week follow-up. and twice for those on waitlist (baseline and 10 weeks after randomization). It is hypothesized that BPS WebSTAIR will be superior to WL on all four outcomes. Mixed Effects Models will be used to evaluate the outcomes.

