**(7.) Methods**

**(a) Study design and approach**

This is a two-condition randomized controlled trial comparing BPS webSTAIR to WL. Participants will be enrolled in a 2:1 ratio (BPS webSTAIR vs. WL). Participants will be recruited from among users of the Vets Prevail website. A special effort will be made to enroll women Veterans via relevant ads on Facebook and other social media. Vets Prevail is responsible for enrolling 300 Veterans (200 into webSTAIR, 100 into WL). As noted in the study contract, enrollment is defined as the number of participants who have been accepted into the study and randomized into a treatment condition. Vets Prevail is responsible for recruiting and screening veterans and alerting NCPTSD RA to make phone contact with Veteran at all relevant assessment periods (baseline, post-tx and follow-up). The NCPTSD RA will facilitate completion of verbal informed consent, describe program including goal of completing program in 10 weeks answer questions about the study and motivate engagement in the program. The NCPTSD RA will then read through the baseline questions and document the answers. At the end of the call, the RA will recommend to the Veteran that they enter the Welcome Module and provide guidance to them at that time if they are ready to begin program.

Individuals accepted into the study will either be provided with access to BPS webSTAIR or placed on waitlist. Participants in BPS webSTAIR will complete a posttreatment assessment and 2-month follow-up. Participants in the WL condition will

complete a second assessment at 10th week, conclude their involvement in the study and be offered the Vets Prevail coping program including the use of webSTAIR.

In the BPS webSTAIR condition, participants will first complete a welcome module to orient them to the program. After randomization, participants will have 10 weeks to complete the 6 modules. Every time the Veteran logs on they will have the opportunity to engage with a Veteran peer for support through the web program. Contacts can last for up to an hour. Veterans will receive a series of automated reminders and engagement emails that the Vets Prevail program sends at various points in the program.

(b) Population and sample, including control group, if applicable.

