**(d) Analysis Plan.**

**Overview:** The equivalence of the treatment conditions on baseline variables (demographics and psychological variables) will be assessed and controlled (if necessary) in the final analyses. Other preliminary analyses will include examination of distributional properties of the measures. We will use transformations to improve distributions when necessary. Missing data patterns (from missed assessments and from dropout) will be examined and compared between conditions. Mixed Effects Models (MEMs) will be used to evaluate differences between the two treatments over time with time as a main effect and treatment-by-time as an interaction term. Participants will be random.

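### Read literally, the plan's mixed model is a random-intercept model, under which the standard error of the week-10 between-arm difference may be too small or too large.

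*Combined protocol and SAP*

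**What the plan says.** Section (7.)(d), Analysis Plan, gives the model in two sentences. The fixed part is: "Mixed Effects Models (MEMs) will be used to evaluate differences between the two treatments over time with time as a main effect", plus "treatment-by-time as an interaction term". The random part is: "Participants will be random". The section does not mention random slopes, a residual covariance structure, the coding of time, a robust standard error, a degrees-of-freedom method or a named contrast. A treatment main effect is not listed.

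The schedule differs by arm. Section (2.) states: "Assessments will occur three times for those in webSTAIR: baseline, post-treatment (10 weeks after randomization) and 8-week follow-up". For waitlist the assessments occur "twice for those on waitlist (baseline and 10 weeks after randomization"). Sections (5.) and (7.)(a) agree. The follow-up falls 10 + 8 = 18 weeks after randomization, and only webSTAIR has it.

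Section (7.)(a) sets the numbers: "Vets Prevail is responsible for enrolling 300 Veterans (200 into webSTAIR, 100 into WL"). It defines enrollment as acceptance and randomization, so the arms are 200 and 100. The primary outcome is the PCL-5 (section (5.)).

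**The concern.** Participant is the only random term named. An analyst who follows the sentence as written fits a random intercept with independent, equal-variance residuals. That model has a single within-person variance, pooled over every pair of visits in both arms, and it sets the standard error of the week-10 difference in change.

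If the follow-up is in the model, webSTAIR supplies 200 × 2 = 400 of the 500 within-person degrees of freedom, and two of its three visit pairs involve a visit that waitlist lacks. The standard error of a baseline-to-week-10 comparison then depends partly on how the follow-up correlates with the other visits. Separately, one pooled variance gives the wrong weights if change is more variable in one arm than the other, and 2:1 allocation makes this matter.

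The p-value and confidence interval of the trial's main comparison are at stake. A covariance structure chosen after the data are seen would also leave analytic freedom.

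**Working it through.** The plan states no standard error, SD, correlation, alpha or power, so there is no figure of its own to reproduce.

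**Inputs from the documents.** 200 webSTAIR participants with three visits; 100 waitlist participants with two.

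**Assumptions.** Two-sided 5% test, complete data, categorical time, separate means for each arm and visit, large samples. SDs and correlations are assumed and varied.

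**Formulas.** Let V01, V02 and V12 be the variances of within-person differences in webSTAIR (weeks 0–10, 0–18, 10–18), and W01 the week 0–10 variance in waitlist.

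- Pooled within-person variance: s² = [400 × (V01 + V02 + V12)/6 + 100 × W01/2]/500
- Model SE = √[2 s² (1/200 + 1/100)]
- True SE = √[V01/200 + W01/100]
- True error = 2 × [1 − Φ(1.96 × model SE/true SE)]

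Full likelihood fits of the random-intercept model at its large-sample limit agree with these formulas to within about 0.1 percentage point of error in the cases below.

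**One case in full.** SD 15 throughout; correlations 0.50 (weeks 0–10), 0.45 (0–18), 0.80 (10–18); waitlist 0.50.

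- V01 = 450 × 0.50 = 225; V02 = 450 × 0.55 = 247.5; V12 = 450 × 0.20 = 90; W01 = 225
- s² = (400 × 562.5/6 + 100 × 112.5)/500 = (37,500 + 11,250)/500 = 97.5
- Model SE = √(2 × 97.5 × 0.015) = 1.71; true SE = √(1.125 + 2.25) = 1.84
- Ratio 0.931; true error 6.8%

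**Other cases, follow-up in the model.** Correlations are in the order 0–10, 0–18, 10–18. Baseline SD is 15. Waitlist has the same 0–10 correlation unless noted.

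| Assumption | SE ratio | True error |
|---|---|---|
| Compound symmetry, 0.6 throughout | 1.00 | 5.0% |
| Equal SDs, 0.6/0.5/0.7 | 1.00 | 5.0% |
| Equal SDs, 0.6/0.5/0.8 | 0.97 | 5.8% |
| Equal SDs, 0.5/0.5/0.8 | 0.92 | 7.3% |
| Equal SDs, 0.6/0.36/0.6 | 1.08 | 3.5% |
| Equal SDs, 0.7/0.5/0.7 | 1.09 | 3.3% |
| 0.50/0.45/0.80; post-baseline SD 13 webSTAIR, 17 waitlist | 0.87 | 8.8% |
| 0.50/0.45/0.80; post-baseline SD 18 webSTAIR; waitlist SD 15, correlation 0.7 | 1.09 | 3.3% |

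**What fixes the direction.** With equal SDs and the same week 0–10 correlation r01 in both arms, s² is proportional to 400(1 − r̄) + 100(1 − r01), where r̄ is the mean of the three webSTAIR correlations. A correct SE needs 500(1 − r01). The model SE is therefore too small only when r̄ > r01, that is, when the average of r02 and r12 exceeds r01. For 0.50/0.45/0.80 that average is 0.625 > 0.50 (too small). For 0.6/0.5/0.7 it is 0.60 = 0.60 (exact). For 0.6/0.36/0.6 it is 0.48 < 0.60 (too large).

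**Only the two shared visits.** Now s² = (200 × V01/2 + 100 × W01/2)/300. With the same covariance in both arms the ratio is 1.00 whatever the correlation. In the 13/17 case it is 0.957 (6.1%). In the 18/15 case it is 1.12 (2.8%), so there the third visit moves the ratio closer to 1. In these two cases, unequal variances cause error even without the follow-up.

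**Common baseline mean.** The plan lists no treatment main effect, so this variant is possible. For 0.5/0.5/0.8 the ratio is 0.94 (6.7%). With two shared visits, a common covariance, correlation 0.5 and an SD rising from 1 to 1.2 (in baseline SD units), it is 0.92 (7.1%).

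**Not a bound.** A less favorable assumed pattern (webSTAIR 0.7/0.7/0.8 with constant SD; waitlist SD rising from 1 to 1.2, correlation 0.5) gives 0.81 (11.2%).

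**The case against.** The strongest reply is that the plan does not state a compound-symmetry model. Its sentence on participants excludes neither random slopes nor a structured residual, and nothing says that the follow-up enters the comparative model. Since waitlist has no such visit, comparing the arms on the two shared visits is a natural reading. With separate baseline means and a common covariance, the standard error is then exactly right. This stands, and it is why the conclusion is conditional.

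A reader might infer that the week-10 standard error is wrong, or that it is too small whenever variances are equal because weeks 10 and 18 correlate more than weeks 0 and 10. The documents support neither. The inference overlooks the week 0–18 pair, whose lower correlation raises the pooled variance: at 0.6/0.5/0.7, weeks 10–18 correlate more than weeks 0–10 and the error is still 5.0%. Nor can every miscalibration be laid on the third visit, as the 18/15 case shows.

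The reply does not dispose of the point. Section (5.) places webSTAIR's three assessments and waitlist's two within the same comparative hypotheses, and the random intercept is the simplest reading of the text. Leaving out the follow-up does not protect against arms that differ in the variance of change.

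**Conclusion.** The point holds in conditional form. The literal model is a random intercept. If the follow-up enters it, or if the arms differ in the variance of change, the model-based standard error of the week-10 difference may be too small or too large. In the main worked examples the SE ratio runs from 0.87 to 1.09 and the true two-sided error from about 3% to 9%. These figures rest wholly on assumed SDs and correlations, complete data and large-sample theory. They show possible sizes; they neither predict nor bound the error. The documents do not establish that the standard error is wrong, or in which direction. They do leave the primary test without protection that would cost almost nothing.

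**What to change.** In section (7.)(d), replace the sentence on participants with a specified repeated-measures model:

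- the week-10 treatment difference as the primary contrast;
- time as categorical;
- an unstructured within-person covariance, estimated by arm, with Kenward-Roger degrees of freedom; or a robust (sandwich) standard error, which meets the same need;
- a statement that the webSTAIR-only follow-up does not define the between-arm comparison.

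The arm-specific covariance has 6 + 3 = 9 parameters against two for the random intercept, which 300 participants support easily. The standard error may be slightly larger: in the equal-SD example it goes from 1.71 to 1.84 points, and the error returns from 6.8% to 5%. No visit, participant or procedure changes.

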**(8.) Duration/Resources**

**Proposed Duration of Study:** The probable duration of the study will be approximately 24 months. We expect that it will take approximately 3 months to build and test the webSTAIR program, obtain IRB approval and hire and train staff, 17 months to recruit the participants and approximately 5 additional months to finish collecting the data (last cohort of participants which will take a maximum of 18 weeks to complete), and approximately 3 months to clean, analyze data and prepare reports.

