## Monthly Gantt Chart – Timeline for tasks and participant

Tasks	M01-03	M04-06	M07-09	M10-12	M13-15	M16-19	M20-23	M24-26	M27-29
Build & Pilot test webSTAIR	3Mo								
IRB Approval	3Mo								
Hire and Train Staff	3Mo								
Enroll Participants						17Mo			
Final Follow-Up Data								5Mo	
Data Analysis and Reports									5Mo

**Funding:** Internal NCPTSD funds will be used to cover the costs of participant reimbursement. Participants will be reimbursed \$40 for the baseline assessment, \$60 for the post assessment and \$60 for the 2-month follow-up.

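### Does a stated duration of 24 months, against stages that add up to 28, mean that 300 Veterans cannot be enrolled and followed?

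*Combined protocol and SAP*

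**What the plan says.** Section (8.) Duration/Resources opens with the total: "The probable duration of the study will be approximately 24 months". It then lists the stages. Set-up comes first, at about 3 months for software, ethics approval and staffing. Next are recruitment and the remaining follow-up: "17 months to recruit the participants and approximately 5 additional months to finish collecting the data". The last stage is given as "approximately 3 months to clean, analyze data and prepare reports". A parenthesis on the data-collection stage describes the "last cohort of participants which will take a maximum of 18 weeks to complete".

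The Monthly Gantt Chart that follows has columns up to M27-29. It labels enrolment as 17 months, final follow-up as 5 months, and the row "Data Analysis and Reports" as 5 months, where the text gives 3 for that work.

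The enrolment target is set elsewhere. Section (7.)(a) makes the recruiting platform responsible for 300 Veterans, 200 on webSTAIR and 100 on waitlist, and counts a participant as enrolled once accepted and randomised.

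**The concern.** A total should equal the sum of its parts, and this one is 4 months short of it. Nor can the stages easily be run side by side to recover the difference, because the data-collection stage is described as additional to recruitment. The chart gives a different end point from the text and a different length for the analysis stage.

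If someone held the trial to 24 months and kept the other stages as listed, recruitment would have to absorb the whole gap. Enrolment would then fall short of 300 or the last follow-up visits would be cut off, and either would cost precision.

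**Working it through.** **Inputs.** From section (8.): set-up 3 months, recruitment 17, remaining data collection 5 (with an 18-week maximum for the last cohort), analysis and reporting 3, stated total 24. From the Gantt chart: column headings from M01-03 to M27-29, and row labels of 3, 17, 5 and 5 months. From section (7.)(a): 300 randomised.

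**Step 1: try to reproduce the stated total.**

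- All four stages in sequence: 3 + 17 + 5 + 3 = 28. The excess over 24 is 4 months, or 4/24 = 17%.
- The same with 18 weeks in place of 5 months: 18 × 7 / 30.44 = 4.1 months, so 3 + 17 + 4.1 + 3 = 27.1.
- Gantt columns: 3 + 3 + 3 + 3 + 3 + 4 + 4 + 3 + 3 = 29.
- Gantt row labels, if no rows overlap: 3 + 17 + 5 + 5 = 30.

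No version that includes all four stages gives 24.

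**Step 2: check the 18 weeks.** A webSTAIR participant has 10 weeks of treatment and an 8-week follow-up: 10 + 8 = 18 weeks. Waitlist participants finish at week 10. The 18-week maximum is therefore right, and the 5-month allowance covers it with some slack (5 − 4.1 = 0.9 months).

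**Step 3: when does participant activity end?** Leave out analysis, which involves no participants.

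- With the 5-month allowance: 3 + 17 + 5 = 25.
- With the 18-week maximum: 3 + 17 + 4.1 = 24.1.

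The whole 17-month recruitment window and complete follow-up of the last person randomised overrun the stated total by 0.1 to 1 month. The one reading of the text that lands close to 24 is set-up, recruitment and 18 weeks, with analysis left out. The total may have been formed that way, but the document does not say so.

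**Step 4: what a hard stop would do.** Suppose that month 24 were a fixed limit, that it also had to contain analysis, and that recruitment took the whole cut.

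- Recruitment window: 24 − 3 − 5 − 3 = 13 months.
- Planned rate: 300 / 17 = 17.6 per month. In 13 months: 13 × 300 / 17 = 229, a shortfall of 71 (71/300 = 24%).
- Rate needed to reach 300: 300 / 13 = 23.1 per month, and 23.1 / 17.6 = 1.31, or 31% faster.

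The arithmetic is correct, but none of the three conditions is in the plan. A loss of power calculated from 229 would rest on the same conditions, and also on a power level and significance level that the protocol does not give.

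**Step 5: does any result depend on the total?** Assessments are timed from randomisation (10 weeks, then 8 weeks later). The Analysis Plan in section (7.)(d) fits mixed-effects models to those assessments and sets no calendar cut-off. Replacing 24 by 28 would leave every one of these elements as it is.

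**The case for a change.** The best case for acting is that this is the protocol's only statement of total duration, in the section on resources, and that a reader cannot tell from it whether the project lasts 24, 28 or 29 months. An approximation can cover one month but not easily four, which is longer than the whole analysis stage. Even if analysis ran entirely alongside follow-up, the stages would still give 25. The correction would cost one sentence and a revised chart.

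Most of this stands. The total and the listed stages disagree, and so do the 3 and 5 months for analysis. Two parts go further than the documents allow. First, the chart labels cannot be added to 30 and called an overrun of the axis, because bar extents are lost in the extracted table and rows may overlap: follow-up in months 22 to 26 and analysis in months 25 to 29 would fit two 5-month bars on the existing axis. Second, no text ties staffing, platform access or approval to 24 months. The funding note under the chart covers only participant payments per assessment.

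**Conclusion.** No change to the plan follows. The stated duration is 4 months below the sum of its stages, and the text and chart differ by 2 months on analysis. These are clerical inconsistencies in a project timeline that is itself given as probable and approximate. They do not show that 300 Veterans cannot be enrolled and followed: recruitment keeps its 17 months, the last participant finishes at about month 24 to 25, and the part left over is mainly desk work. A team that follows the document as written would randomise the same number, follow them for the same time and run the same models.

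This rests on two assumptions: that the stage lengths, which are explicit, govern the conduct of the trial in preference to the rounded total; and that no deadline at month 24 exists outside these documents. If such a deadline did exist, the figures in Step 4 would show the worst case. The timeline can be tidied whenever the document is next edited, but nothing statistical waits on it.

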## Monthly Gantt Chart – Timeline for tasks and participant

Tasks	M01-03	M04-06	M07-09	M10-12	M13-15	M16-19	M20-23	M24-26	M27-29
Build & Pilot test webSTAIR	3Mo								
IRB Approval	3Mo								
Hire and Train Staff	3Mo								
Enroll Participants						17Mo			
Final Follow-Up Data								5Mo	
Data Analysis and Reports									5Mo

**Funding:** Internal NCPTSD funds will be used to cover the costs of participant reimbursement. Participants will be reimbursed \$40 for the baseline assessment, \$60 for the post assessment and \$60 for the 2-month follow-up.

